As part of the work proposed in this grant is to test the Lifestyle Balance Program in other mental health programs, we have already begun disseminating the program locally. What we found when recruiting patients for our current research study is that 50% of the PRRC patients who were recruited for the research study declined. Many were too psychotic to realize that their weight was a problem. Thus, to help the PRRC patients that would not access the research program, nor the MOVE! Program we started to disseminate, in the past three months a weight loss program within the PRRC itself. The PRRC's weight loss programs include weekly classes on wellness, weekly weigh ins with our clinic nurse, and exercise classes that have yielded some positive results. In 6 months, since we started to disseminate our program into our own PRRC, 17 patients who participated in the disseminated weight loss program we began providing in our PRRC have lost up to 5 pounds. Other programs have approached us for help with weight loss in the SMI population including the dual diagnosis treatment program at our facility. We have trained the nurses in that program to provide Lifestyle Balance Classes. Over the past year we began collaborative efforts with our MOVE! Program leaders to be able to provide additional support to the MOVE! Team for patients with SMI who are not doing well in the conventional MOVE! Program. Also, outside of the VA system, [name] is adopting the Lifestyle Balance Program into her clinic at the Didi Hirsch community mental Health Center, as part of her PhD thesis work. The ongoing classes provided in the PRRC by our nurse can also be accessed by the research program and MOVE! graduates and have served to assist them with continued weight loss and/or maintenance. These early experiences in disseminating the lifestyle balance classes and the principles of this weight loss program have shown us that each program will be adopting certain components of our program dependent upon the number of staff and time available of those staff to provide the intervention.

E. Progress Report for Funding Period for Merit Review 2006-2009:

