Initial inter-rater reliability will be maintained for the BPRS, CGI, Ham-D, and QOLS scales by utilizing recordings of taped live interviews -available by DVD - that all raters must assess during the initial start up phase and every 6 months thereafter. Initially each rater will assess 3 tapes and kappa will be determined for inter-rater reliability. Once the study is underway, to prevent rater drift, every 6 months all raters will rate a recorded interview that will be made available to them by DVD.

Inclusion/Exclusion Criteria: Patients recruited for this research study from four different sites will need to commit to a 12 month period of participation. This protocol will have two phases, an initial 2-month intensive phase (weekly classes and individual visits) followed by a 10 month (once per month) maintenance extension phase. Since many patients with SMI live somewhat transient existences, patients included in this study cannot be homeless and must have some type of stable living circumstance. All patients with SMI (e.g. psychotic disorders, schizophrenia, schizoaffective disorder and bipolar illness, post traumatic stress disorder) aged 18-70 who are taking antipsychotic medications, admitted to inpatient wards of the Greater Los Angeles VA Medical Center, Long Beach Medical Center, as well as outpatient programs at all four sites, of the Sepulveda VAMC, and the Los Angeles Ambulatory Care Center, West Los Angeles VA Mental Health Clinic, Schizophrenia Treatment Unit, Domiciliary, Exodus Lodge, and local Board & Cares and residential dual diagnosis treatment programs will be screened for possible participation in this behavioral weight loss program that includes diet, exercise, and Lifestyle Balance classes. We intend to recruit non-veteran females (to increase our representation of females in this research) from the Didi Hirsch Community Mental Health Center, in addition to our women's clinic here at West Los Angeles. Sepulveda VAMC has a large outpatient program, and a partial hospitalization program (that is converting to a PRRC) and MHICM programs from which to recruit patients. LAAC also has a large outpatient mental health program and 3 day treatment/partial hospitalization

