programs (that are converting to PPRCs) from which to recruit. There are 10,000 patients classified as SMI within these three medical centers. Long Beach hospital also has a large outpatient as well as an inpatient program from which to recruit. Long Beach hospital served over 10,000 mental health unique veterans in 2008, of which probably half of these are SMI. To assist doctors in identifying which patients under their care are eligible for our study, we intend to obtain Waiver of HIPAA for screening purposes. With this we can obtain from the VA a list of eligible patients and approach their doctors to notify them of their eligibility and what the program involves so that the doctors can effectively discuss it with those patients and direct them to us. Finally, we intend to utilize social media to spread word of the study, requesting mention of it be made by the GLA VA Facebook page.

One hundred twenty patients clinically determined to require ongoing treatment with SGAs who have experienced 7% or more increase in weight or whose BMI has become greater than or equal to 25 during treatment with an SGA will be randomized to receive either the Lifestyle Balance Program (a MOVE! like behavioral weight loss intervention with psychoeducational classes) or Usual Care. These inclusion criteria have been chosen to selectively recruit only subjects whose adiposity is both clinically pertinent and reasonably construed to be due to the introduction of an antipsychotic. All patients will be asked to sign informed consent. Patients who are unable to give informed consent will not be entered into the study. Subjects with a history of substance abuse or dependence cannot participate in this study unless they are sober for three months. If a patient has a legal conservator, and wants to participate in the study, he or she will need the legal conservator to sign informed consent. If a patient is too medically ill to be involved in any type of exercise or weight loss program he or she will be excluded from the protocol (e.g. a patient with cancer on chemotherapy who is vomiting and losing weight should not be entered into this study).

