E. Procedures for the Usual Care Group: As most psychiatrists are being advised to counsel patients on weight, diet, and exercise, Usual Care will be only some modest counseling. Referral to the MOVE program by their treating psychiatrist would not be discouraged. Patients will be encouraged to exercise and eat a healthy diet, and will be weighed at each visit. No classes on nutrition and no exercise classes will be given to these patients as part of this program. Patients in usual care will be seen on the same schedule as the experimental group, in order to equalize contact time. At every visit, patients will complete a questionnaire about their knowledge of healthy eating habits and nutrition. After 6 months, if patients in the “usual care group” wish to participate in the more rigorous behavioral weight loss program they will be given that opportunity. A de-identified photograph of each participant’s body from the neck down will be taken during visit one and at the end of study.

SCHEDULE OF EVENTS

Visit	Time	Rater	0	1-7	8	9	10	11	12	13	14	15	16	17	18
Week			0	1-7	8	12	17	21	26	30	34	38	43	48	52
Month			0		2	3	4	5	6	7	8	9	10	11	12
Visit Log/Assessment Packet	--	--	X	X	X	X	X	X	X	X	X	X	X	X	X
AHA Exercise Risk Stratification	10	MD	X												
Brief Psychiatric Rating Scale (BPRS)	15	MD	X		X				X						X
CGI	5	MD	X		X				X						X
Hamilton Depression/ Beck Anxiety Scale	20	MD	X		X				X						X
Physical Exam	15	MD	X												X
Structured Clinical Interview for DSM-IV (SCID)	15	MD	X												
Antipsychotic Side-effects Checklist (ASC)	5	C	X		X				X						X
Assessment of Patient Food Preparation Activity	5	C	X		X				X						X
Biopsychosocial/Spiritual Wellness Self Appraisal (BPSS)	5	C	X		X				X						X
Demographics	10	C	X												

EXIT interview	5	C														X
Fidelity Checklist Change Assessment	10	Proj. Mgr	X						X							X
Framingham Hard Coronary Heart Disease	5	C	X													X
Healthy Lifestyle Balance Knowledge Quiz	15	C	X		X				X							X
Informed Consent Video	30	--	X													
Informed Consent Quiz	15	C	X						X							X
Labs: Lipid Profile, fasting glucose, HgbA1C, insulin/ HOMA calculation, c-reactive protein, microalbumin, creatinine	10	Lab	X		X				X			X				X
Lifestyle Habits Questionnaire	10	C	X	X	X	X	X	X	X	X	X	X	X	X	X	X
Motivational Interview	5	C	X		X				X							X
Quality of Life Scale	15	C	X													X
SAIQ- Insight Measure	10	C	X		X				X							X
Telephone Contact Assessment (as needed)	5	C														

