It provides valid statistics even in cases where there are more potential predictors than observations, and allows us to include all demographic, psychosocial, psychiatric and medical data known at baseline as potential predictors. The results of this analysis will suggest which patients are most likely to profit from further interventions, and it will also characterize the most at risk patients.

c) Subjects will continue to give meaningful, informed consent to participate throughout the study. They will see no significant decrease in their score on the informed consent quiz given every 6 months.

Analysis plan: A general linear model (GLM): ANOVA will be performed to compare the informed quizzes score results at 0, 6, and 12 months during the subjects' participation in the study.

5. Power Analysis: All calculations are based assuming a conventional medium effect size ($f=.25$, Cohen 1988); and a two-tailed alpha set at 0.05. Tuomilehto et al. estimated the SD of weight loss at roughly 5 kg across several treatment conditions (lifestyle changes vs. control) (76). A medium effect would thus translate into a group difference of about 2.5 kg or about 5.5 pounds. With an enrollment of $N=120$ and an estimated attrition rate of 45% we expect that at least 66 subjects will provide complete the study and provide 4 data points. The power analyses below are based on a sample size of $N=66$, i.e. this is a very conservative estimate due to the fact that the mixed linear model allows us to include cases with missing values in the analyses and that while they don't provide as much information as complete cases they still provide some information and will increase power. For the between-group comparisons, $N=66$ yields power=.7199 for main differences between groups if we assume that the within subject correlation is $r=.50$. Power to test for the difference in outcome trajectories of time – our main outcome variable is 0.99, and even if the effect is as small as $f=0.15$ we will have sufficient power to distinguish between the trajectories of the two treatment groups (power=0.83) insuring that we will get significant, insuring that we Preliminary data analyses shows that these assumptions are quite conservative and that effect sizes seem to be slightly larger than projected, suggesting that the final power will exceed the estimates presented here.

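### Some recruitment sources already give Lifestyle Balance classes or parts of them, and no stated criterion, schedule item or analysis covers that exposure in usual care

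*Combined protocol and SAP*

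**What the plan says.** **The comparator.** Section V.E limits usual care to modest counseling and weighing, and states: "No classes on nutrition and no exercise classes will be given to these patients as part of this program". It does not discourage referral to MOVE! by the treating psychiatrist. Controls may ask to enter the full program after six months.

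**Where the program already runs.** Section IV.D.3 (Pilot Study 3) describes local dissemination. The lead-site PRRC's "weight loss programs include weekly classes on wellness, weekly weigh ins with our clinic nurse, and exercise classes". Of the dual diagnosis program at the lead facility it says: "We have trained the nurses in that program to provide Lifestyle Balance Classes". A community mental health center outside the VA is adopting the program. Section II.E adds that individual and group MOVE!-like classes were built into the PRRC.

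**Where patients come from.** The Inclusion/Exclusion Criteria in section V cover inpatient wards and outpatient programs at all four sites, and "local Board & Cares and residential dual diagnosis treatment programs will be screened for possible participation". Non-veteran women are to be recruited from the same community center.

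**What is controlled or recorded.** The criteria address, among other things, housing, age, antipsychotic treatment, weight gain or BMI, consent, sobriety and medical fitness. None mentions Lifestyle Balance, PRRC or MOVE! attendance, or randomisation in the first study. Randomisation is by individual patient and stratified by medication (N, Stratification). Section V.L has drug changes documented. The Schedule of Events names no item for outside classes, and sections N.1 to N.4 plan no related covariate or sensitivity analysis.

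**The concern.** The trial estimates the difference between the program and usual care. If some controls attend the same classes, or the same exercise sessions, through their own unit, the contrast for those patients is the program against part of itself. The example timetable for the West Los Angeles site lists PRRC exercise classes as the intervention's exercise options, and a control who attends that PRRC could use the same timetable.

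The bias runs toward no difference, on knowledge (primary hypothesis a), lifestyle change and weight alike. It can begin at baseline, so it is separate from the disclosed six-month option. If exposure is not recorded as it happens, the report cannot say how much of a small difference reflects a weak program and how much a treated control arm.

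Earlier exposure matters for a different reason. Randomisation balances it between arms in expectation, but a patient who has already taken the classes has less left to learn. The trial then partly estimates the effect of a second course.

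**Working it through.** **Inputs, from N.5 (Power Analysis) unless noted**

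- "All calculations are based assuming a conventional medium effect size", f = 0.25, "and a two-tailed alpha set at 0.05".
- The cited source "estimated the SD of weight loss at roughly 5 kg across several treatment conditions", so a medium effect is about 2.5 kg or 5.5 lb.
- 120 enrolled and 45% attrition: 120 × 0.55 = 66 completers, with 4 time points and r = .50.
- A fallback effect of f = 0.15 for the trajectory test.
- 30 patients at each of four sites (section V.A).
- Not given, so assumed: 1:1 allocation within site, equal attrition across sites, and the exposed share of controls, c.

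**Reproducing the plan's power**

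Main effect: λ = f²·N·m / (1 + (m−1)r) = 0.0625 × 66 × 4 / 2.5 = 6.6 on F(1, 64). Power is .716, against the stated .7199.

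Trajectory (group by time): λ = f²·N·m / (1−r) on F(3, 192).

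- f = .25: λ = 0.0625 × 264 / 0.5 = 33. Power is .999, against the stated 0.99.
- f = .15: λ = 0.0225 × 264 / 0.5 = 11.88. Power is .828, against the stated 0.83.

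The plan's figures reproduce, and they contain no allowance for exposed controls.

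**Dilution**

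If a share c of controls gains the full program effect, the mean difference is multiplied by (1−c) and λ by (1−c)².

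**A bound for c from the documents.** The VA units where section IV.D.3 places the program are at the lead site. With 30 patients there and 1:1 allocation, that site supplies about 15 of 60 controls, so c is at most 15/60 = 25% from lead-site exposure. At c = .25, (1−c)² = .5625, which gives λ = 3.7125 (main effect), 18.5625 (trajectory, f = .25) and 6.6825 (trajectory, f = .15).

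| Exposed share c | Difference | Main-effect power | Trajectory, f=.25 | Trajectory, f=.15 |
|---|---|---|---|---|
| 0% | 5.5 lb | .716 | .999 | .828 |
| 10% | 4.95 lb | .625 | .995 | .734 |
| 25% | 4.1 lb | .475 | .961 | .558 |

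The 25% row takes every lead-site control as exposed and as gaining the whole effect. Actual lead-site dilution should be smaller.

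**The case against.** Much of the case on the other side stands.

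- **Scope.** The documented overlap is at the lead site and one community center. Section V.B calls the other three sites new, with coaches still to be trained and exercise options still to be developed. The eligibility text does not name the lead-site PRRC, which comes in only through outpatient programs. It is likely, but not stated, that the dual diagnosis program with trained nurses is one of the residential programs screened. A reader might infer that controls throughout the trial receive the program, or that half of them do; the documents give no basis for either.
- **Dose.** Section IV.D.3 expects each adopting program to take up only some components. The tested package adds individual coaching, motivational interviewing, contracts, diaries, caregiver sessions and rewards (section V.D).
- **Power.** N.5 treats the difference in trajectories as its main outcome, and that test at f=.25 is hardly affected. Quoting only the main-effect figure would mislead. The loss is real if the effect is near f=.15.
- **Recording.** A visit log, an assessment packet and a Lifestyle Habits Questionnaire are completed at every visit, and the forms are in appendices not available here. One may say that no stated item records outside classes, but not that nothing does.
- **First study.** It is tempting to say that all 123 earlier randomisees took the classes. Only its intervention arm was assigned them.
- **MOVE!.** In an effectiveness trial, permitted referral is a declared part of usual care and not hidden contamination.

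None of this fills the gap. A usual-care arm may contain background care, but the report should be able to say what that care was, especially where it may include the tested classes.

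**Conclusion.** The point holds as a cheap improvement. Some named sources give or are adopting Lifestyle Balance classes or parts of them, the control restriction reaches only study-delivered classes, and no stated criterion, schedule item or analysis deals with current or earlier exposure. The result is a bias toward no difference of unknown size.

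At the lead-site upper bound of 25%, the 5.5 lb difference shrinks to about 4.1 lb. Main-effect power falls from .72 to about .48, trajectory power at f=.25 stays about .96, and trajectory power at f=.15 falls from .83 to about .56. This rests on 1:1 allocation, attrition equal across sites, and full benefit in every exposed control. Exposure among community-center recruits would add to it only if they are enrolled at another site, which the documents do not say.

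A reader might go further and conclude that a null result could not be interpreted at all. The documents do not support that: the overlap is local and probably partial, and the main trajectory test at the planned effect tolerates it.

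**What to change.** 1. **Eligibility (Inclusion/Exclusion Criteria).** Exclude people who were randomised in the first study, and people who currently attend or have recently completed Lifestyle Balance classes, with the look-back period stated.
2. **Recording (Schedule of Events).** Add one item to the visit log in both arms, at baseline and every visit, that counts outside Lifestyle Balance, PRRC wellness, MOVE! and exercise classes. Report it by arm.
3. **Analysis (N.4).** Pre-specify a sensitivity analysis by exposure. Since attendance after randomisation is not itself randomised, present it as supportive.
4. **Leave in place.** Keep MOVE! referral as a recorded part of usual care, and do not bar whole recruitment units. Barring units could remove the community center, which is a named route to more women; the first study had 10 among 123.

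The cost is a protocol amendment, one extra log item and a slightly smaller recruitment pool. The pool can bear it: "There are 10,000 patients classified as SMI within these three medical centers", with Long Beach in addition, for 120 places. The exclusion does not stop a control from joining outside classes later, which is why the log item is needed as well.
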